## SCHEMA

TNBC – triple negative breast cancer; CNS – central nervous system; SRS – stereotactic radiation to brain metastasis;

- \*D1 of Atezolizumab (A) will be administered 2-7 days before the initiation of SRS.
- Bx1 – Baseline tumor biopsy will be obtained within 28 days of starting Atezolizumab.
- Bx2 – Reassessment biopsy will be obtained between C2D1-C2D21.
- Imaging will be performed at screening within 4 weeks before starting Atezolizumab. Tumor assessments, including brain magnetic resonance imaging and computed tomography of the chest, abdomen and pelvis, will be performed every 6 weeks ( $\pm 1$  week) for the first 24 weeks on treatment, and every 9 weeks ( $\pm 1$  week) thereafter, with additional scans as clinically indicated.
- **Blood samples will be collected within 7 days before starting treatment (baseline), at day 1 ( $\pm 3$  days) of cycle #3, #5, #9, and at progression or off protocol therapy, whichever comes first.**
- **Cerebrospinal fluid collection will be performed at 3 times points (baseline, before cycle 3, and at progression or off protocol therapy, whichever comes first).**

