## **6. DOSING DELAYS/DOSE MODIFICATIONS**

Dose delays and modifications will be made as indicated in the following table(s). The descriptions and grading scales found in the revised NCI Common Terminology Criteria for Adverse Events (CTCAE) version 4.0 will be utilized for dose delays and dose modifications. A copy of the CTCAE version 4.0 can be downloaded from the CTEP website [http://ctep.cancer.gov/protocolDevelopment/electronic\\_applications/ctc.htm](http://ctep.cancer.gov/protocolDevelopment/electronic_applications/ctc.htm).

Dosing interruptions are permitted in the case of medical / surgical events or logistical reasons not related to study therapy (e.g., elective surgery, unrelated medical events, patient vacation, and/or holidays). Participants held for these reasons are required to resume therapy within 3 weeks of the scheduled interruption. The reason for interruption must be documented in the participant's medical record.

If there are dosing delays for any reason, all study assessments are to be delayed in the same fashion, such that that scans and other assessments occur in conjunction with cycles of treatment.

No dose reductions are allowed for atezolizumab.

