#### 6.1.1 Guidelines for Dosage Modification and Treatment Interruption or Discontinuation

There will be no dose reduction for atezolizumab in this study. Patients may temporarily suspend study treatment for up to 84 days beyond the scheduled date of delayed infusion if study drug-related toxicity requiring dose suspension is experienced. If atezolizumab is held because of AEs for >84 days beyond the scheduled date of infusion, the patient will be discontinued from atezolizumab and will be followed for safety and efficacy as specified in Section 5.5.

Patients should be assessed clinically for toxicity prior to, during, and after each infusion. Any toxicity associated or possibly associated with atezolizumab treatment should be managed according to standard medical practice. Additional tests, such as autoimmune serology or biopsies, may be used to determine a possible immunogenic etiology. Although most irAEs observed with immunomodulatory agents have been mild and self-limiting, such events should be recognized early and treated promptly to avoid potential major complications. Discontinuation of atezolizumab may not have an immediate therapeutic effect, and there is no available antidote for atezolizumab. In severe cases, immune-related toxicities may be acutely managed with topical corticosteroids, systemic corticosteroids, mycophenolate, or TNF $\alpha$  inhibitors.

Management of hepatitis/transaminitis, colitis, rash, and hypothyroidism are presented in this section as they have been observed in this study and are potentially immune related.

Dose interruptions for reasons other than toxicity, such as planned surgical procedures, may be allowed, with prior PI approval. The interruption should not be greater than 84 days.

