**Table 1 Dose Modification Guidelines for Gastrointestinal Toxicity**

Toxicity	Description	Management
Diarrhea and/or Colitis	Grade 1	
 
• Continue atezolizumab.
 
• Initiate symptomatic treatment
 
• Endoscopy is recommended if symptoms persist for > 7 days
 
• Close monitoring.
 

	Grade 2	
 
• Hold atezolizumab
 
• Initiate symptomatic treatment
 
• For recurrent events or events that persist > 5 days: start Prednisone 60 mg/day or equivalent.
 
• When symptoms improve Grade <math>\leq 1</math>, resume atezolizumab               
 
○ Corticosteroids must be tapered over <math>\geq 1</math> month to <10 mg/day oral prednisone or equivalent before resuming.
 
 
 
• Atezolizumab may be resumed if the event improves to Grade <math>\leq 1</math> within 12 weeks, and corticosteroids have been reduced to the equivalent of prednisone <math>\leq 10</math> mg/day.               
 
○ Atezolizumab may be withheld for a longer period of time (i.e., >12 weeks after event onset) to allow for corticosteroids (if initiated) to be reduced to <math>\leq 10</math> mg/day oral prednisone or equivalent. The acceptable length of the extended period of time must be determined by the PI
 
 
 

	Grade 3	
 
• Hold atezolizumab.
 
• Treat with IV steroids (1-2 mg/kg/day methylprednisolone or equivalent) and convert to oral steroids (prednisone 60 mg/day or equivalent) after improvement. When symptoms improve to Grade <math>\leq 1</math>, taper steroids over <math>\geq 1</math> month               
 
○ If event resolves to <math>\geq</math> Grade 1, restart atezolizumab
 
 
 
• If event does not resolve to > grade 1 within 12 weeks of holding, permanently discontinue               
 
○ If the subject was unequivocally deriving clinical benefit, the subject may be rechallenged as
 
 
 

	
determined by the PI.
 
 
• Gastroenterology referral and confirmation biopsy
 

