Atezolizumab		X			X		X	X		X	X			
Post RT Follow-up Visit u											X u			
Survival Status r														X

**Atezolizumab: 1200mg given IV q3 weeks on Day 1 of each cycle + Stereotactic Radiation: radiation will start 2-7 days after the first dose of atezolizumab**

- a. Stereotactic radiation planning appointment must occur at least 7 days prior to initiating radiation
- b. Medical history includes clinically significant disease, surgeries, and cancer history (including prior cancer therapies and procedures).
- c. A complete physical examination, including neurological examination, will be performed at screening. A limited physical exam, to include a neurological exam, will be performed at subsequent Day 1 visits.
- d. Participants will be seen by a radiation oncologist on day 1 of stereotactic radiation and 10 days after radiation completion (+/- 4 days).
- e. Vital signs to include: heart rate, systolic and diastolic blood pressures while the patient is in a seated position, respiratory rate, and temperature.
- f. Selected medications of interest received within 28 days before the first dose of trial treatment and 30 days after the last dose of trial treatment, including dosage, frequency, route, and dates of administration will be documented
- g. T-1 weighted perfusion MRI will be used. Screening MRI must be done within 14 days of the radiation initiation. Subsequent assessments should be done during the last 15-21 days of a cycle, q6weeks for the first 24 weeks (i.e. C2, 4, 6, 8) and then can be reduced to q9 weeks (i.e. C11, 14, 17, etc). If progression is suspected, an unscheduled assessment is permitted. An objective response (CR, PR) should be confirmed by repeat assessments 4-6 weeks after initial finding. Patients with CNS PD are allowed to continue on study for 4-6 weeks to confirm PD on MRI. For those taken off-study for reasons other than progressive disease in the CNS, assessments should continue to be repeated every 6-12 weeks until progression or beginning a new cancer therapy regimen. It is understood that it may not always be feasible for patients to return for restaging evaluation after coming off protocol therapy; however, it is strongly encouraged. Failure to complete CNS restaging after a patient has been taken off protocol therapy will not constitute a protocol violation.

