## 11. MEASUREMENT OF EFFECT

In this study, response and progression in the CNS and in non-CNS sites will be evaluated and recorded separately in this trial. For the purposes of this study, participants should be re-evaluated for response every 6 weeks for the first 24 weeks and then every 9 weeks thereafter. For participants who achieve a sustainable response after 1 year on protocol therapy, re-evaluation can be performed every 12 weeks.

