### 13.2 Sample Size, Accrual Rate and Study Duration

The primary endpoint is bi-compartmental PFS according to RANO-BM criteria. A sample size of 45 was chosen to achieve 80 % power to detect a difference between the null hypothesis median PFS of 2 months and alternative of 3.5 months at a one-sided type I error of 0.05.

The null hypothesis was derived from two sources: First, a prospective trial testing the combination of irinotecan and iniparib in patients with metastatic triple-negative breast cancer and new/progressive brain metastases reported a median time to progression (which included both intracranial and extracranial progression) of 2.14 months [Anders *et al.*, 2014]. Next, in a retrospective study describing outcomes of breast cancer patients after initial stereotactic radiation, time to intracranial progression was significantly shorter in patients with triple-negative breast cancer, relative to the luminal A subtype (HR 28.0 in multivariable model,  $p=0.003$  [Dyer *et al.*, 2012]. Although the numbers are small, the point estimate for the time to intracranial progression in the triple-negative subset was 2.5 months [Dyer *et al.*, 2012].

Anticipated accrual of approximately 2 patients per month, it will require approximately 24 months of patient accession to reach 45 patients. The primary analysis of PFS and OS will be

time-driven and performed after 6 months of additional follow-up.

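### Section 6 lets the first tumor scan slide with a dosing delay, possibly past day 61 where the primary PFS test is read, while the Schema and Section 11 hold it at 6 weeks

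*Combined protocol and SAP*

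**What the plan says.** Section 13.2 sets a "null hypothesis median PFS of 2 months and alternative of 3.5 months at a one-sided type I error of 0.05", with 45 patients and 80% power. Sections 13.1 and 13.5 measure PFS from the first atezolizumab dose and date radiologic progression at first detection. They also count death and unequivocal progression of non-measurable disease as judged by the treating physician. Section 13.5 tests the median with a Brookmeyer-Crowley-like test on the Kaplan-Meier curve.

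Imaging dates are set in two ways.

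- **By calendar.** The Schema says tumor assessments "will be performed every 6 weeks", within 1 week, for the first 24 weeks. Section 11 says "participants should be re-evaluated for response every 6 weeks for the first 24 weeks".
- **By cycle.** Section 10, footnote g: "Subsequent assessments should be done during the last 15-21 days of a cycle, q6weeks for the first 24 weeks", naming cycles 2, 4, 6 and 8. Footnote h does the same for body imaging. Section 6 adds: "If there are dosing delays for any reason, all study assessments are to be delayed in the same fashion", so that scans stay aligned with treatment cycles.

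On the length of delays, Section 6 requires dosing to resume within 3 weeks after an interruption unrelated to study therapy. For toxicity, Section 6.1.1 says "Patients may temporarily suspend study treatment for up to 84 days beyond the scheduled date of delayed infusion". On extra imaging, footnote g says "If progression is suspected, an unscheduled assessment is permitted"; it does not require it. Section 13.5 has no rule for a late or missing scan.

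**The concern.** Testing a 2-month median amounts to reading the Kaplan-Meier curve at one time point, and only one scheduled scan comes before it. If that scan slides past the read-out, a patient who would have been found to have progressed is still event-free on that day. This happens because nobody looked, not because the disease was controlled.

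The delays long enough to matter are mainly toxicity holds. A hold could then pass for delayed progression in a single-arm trial, which has no control group delayed in the same way. At stake is the one-sided 5% error of the primary test. Separately, sites have two incompatible imaging rules once cycle 2 is held for long.

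**Working it through.** **Inputs from the protocol.** n = 45, medians 2 and 3.5 months, one-sided 0.05 (13.2); test and event dating (13.1, 13.5); scan dates (Schema, 10, 11); delay rules (6, 6.1.1).

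**Assumptions, not in the protocol.** The number *d* of patients first scanned after day 61; the share *q* of early events found other than by a scheduled scan; no loss to follow-up before day 61; and a null in which 50% are progression-free at day 61 when the first scan is on time. The analysis comes 6 months after accrual ends, so there is no administrative censoring before day 61.

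**1. The plan's own figure.** For an exponential alternative, S(2 months) = 0.5^(2/3.5) = 0.673. Power = Φ[(0.673 − 0.5)/√(0.673 × 0.327/45) − 1.645] = 79.6%. This reproduces the stated 80% and supports reading the test as S(2 months) against 0.5.

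**2. Read-out day.** 2 × 365.25/12 = 60.9, so day 61.

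**3. On-time scans, with cycle 1 day 1 as day 1.** Cycle 2 days 15-21 are days 21 + 15 = 36 to 21 + 21 = 42. Cycle 4 days 15-21 are days 63 + 15 = 78 to 63 + 21 = 84. The Schema's window gives 42 ± 7 = 35-49 and 84 ± 7 = 77-91. Either way, one scheduled scan precedes day 61.

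**4. Delay of cycle 2 day 1.**
- The two imaging rules part: 49 − 36 = 13, so after more than about 2 weeks no cycle-linked date lies inside the Schema's window.
- The first scan passes day 61: 61 − 42 = 19 to 61 − 36 = 25, so a delay of more than 19 days (scan planned for cycle day 21) to more than 25 days (cycle day 15).
- The 3-week limit reaches this only late in the window: 42 + 21 = 63, but 36 + 21 = 57. The 84-day allowance exceeds every threshold.

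**5. Rejection rule.** With no censoring, the Kaplan-Meier estimate at day 61 is x/45. Greenwood variance at the estimate rejects from x = 28 (z = 1.69; 27 gives 1.37). The log-log form rejects from x = 29 (z = 1.81). Section 13.5 does not say which form the test takes, so both are shown.

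**6. Size.** The *d* late patients are progression-free at day 61 with probability 1 − 0.5q, and the other 45 − d with probability 0.50. Exact binomial sums give the table below. For example, with d = 2 and q = 0 the first rule needs at least 27 of the remaining 43.

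| Late first scans (of 45) | q = 0: ≥29 / ≥28 | q = 0.4: ≥29 / ≥28 |
|---|---|---|
| 0 | 3.6% / 6.8% | 3.6% / 6.8% |
| 1 | 4.8% / 8.7% | 4.3% / 7.9% |
| 2 | 6.3% / 11.1% | 5.2% / 9.3% |
| 3 | 8.2% / 14.0% | 6.1% / 10.8% |

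**7. Shorter delays.** A first scan that is late but still before day 61 finds slightly more events. Take exponential PFS with S(42) = 0.50 and 10% of patients delayed. A 7-day delay gives S = 0.9 × 0.5 + 0.1 × 0.5^(49/42) = 0.4945 and size 3.1-5.9%. A 14-day delay gives S = 0.4897 and size 2.7-5.1%. One patient past day 61 (q = 0.4) together with four delayed 14 days gives 3.3-6.2%, just below the no-delay figures.

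**The case against.** The strongest reply is that few patients can be affected. Only a delay of cycle 2 moves the first scan. Several severe toxicities call for permanent discontinuation (with investigator exceptions in some rows), and Section 10 then asks for an off-treatment visit with imaging within 30 days of the last dose. After a single dose that is about day 31. Toxicity work-ups bring imaging of their own. Section 2.3.2.2 reports related Grade 3 or higher events in 12.4% of patients over the whole of treatment, not in the first cycle, although Grade 2 holds are not in that figure. The choice between the two rejection rules (3.6% or 6.8%) matters more than one late scan, which adds 1.2 to 1.9 points with no off-scan events. Linking scans to cycles is also deliberate.

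Most of this stands. It argues for small counts and for the q = 0.4 column. It does not settle which imaging rule applies, and extra scans on suspicion are permitted, not required.

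Stronger readings are tempting, but the documents do not support them:

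- **That reading the test at the first scan is itself an error.** Progression is dated at first detection. If 2 months is a detected median on this schedule, the error is near nominal.
- **That the benchmark medians of 2.14 and 2.5 months come from a different scan schedule and so distort the error.** Section 13.2 does not give the source studies' assessment intervals, so neither a mismatch nor its direction can be shown.
- **That toxicity holds in general push the scan past day 61, because Table 1 says "Corticosteroids must be tapered over" at least a month.** That line concerns Grade 2 diarrhea or colitis treated with steroids, and the resulting scan date depends on when the taper began.
- **That power is safe in any case.** The 29-of-45 rule gives 71.8% under the plan's exponential alternative. If PFS at the first scan is 0.60 and then flattens, power is 33-44%, even though the median lies beyond the second scan.

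**Conclusion.** The point holds in a limited form. The conflict between Section 6 and the Schema and Section 11 is plain in the text and bears on the primary endpoint. Under Section 6, a cycle 2 delay of more than 19-25 days leaves a patient counted as progression-free at day 61 without a scheduled scan, unless there is a death, physician-judged progression, or an unscheduled or off-treatment scan.

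The size of the effect is conditional. With one to three late first scans, the error is 4.8-8.7% up to 8.2-14.0% if nothing is found off-scan, and 4.3-7.9% up to 6.1-10.8% if 40% of events are, against 3.6-6.8% with none. These counts are assumptions. A reader might infer that delays always inflate the error; shorter ones pull it down, so the net direction depends on a mix of delays that the documents do not give. It is worth correcting because the bias from long holds is tied to toxicity and is cheap to remove.

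**What to change.** Keep the sample size, the hypotheses, alpha and the primary test.

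1. In Section 6, exempt tumor imaging from the clause that delays assessments with dosing. State in Sections 10 (footnotes g and h) and 11 that, for the primary endpoint, brain MRI and body imaging are timed from cycle 1 day 1 whether or not dosing is delayed: every 6 weeks within 1 week for the first 24 weeks, then every 9 weeks. No dosing rule changes.
2. In Section 13.5, commit to reporting the number of patients with no scan by day 61.
3. Sections 6 and 6.1.1 also differ on how long a non-toxicity interruption may last (3 weeks against 84 days). The authors should reconcile them; this review takes no view on which is right.

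With calendar timing, the latest on-window first scan is day 49, before the read-out, and the size is back at 3.6-6.8%. The cost is a few text changes and an occasional imaging visit separate from dosing for a patient on hold. No extra patients are needed.

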### 13.3 Stratification Factors

N/A

### 13.4 Interim Monitoring Plan

A safety run-in analysis will be performed after the first 6 patients are enrolled and have completed the assessment period for dose-limiting toxicity (DLT). The DLT assessment period encompasses the period from first dose of atezolizumab until Cycle 3 Day 1, to allow sufficient time from stereotactic radiation treatment to assess for DLT. If there are 3 or more dose-limiting toxicity (DLTs) in the first 6 patients included, the study will be closed to further enrollment. If this occurs, then any plans to re-open the study with a modified treatment plan will need to be formally reviewed and approved by the sponsor and by the DF/HCC SRC/IRB prior to activation. If there are less than 3 DLT within the first 6 patients enrolled, then the study will proceed to full accrual. All patients who receive at least one dose of study drug will be included in the efficacy analysis.

Table: Probability of continuing enrollment with  $\leq 2$  DLTs out of 6 subjects.

	Safety run-in using 6 subjects						
True DLT rate	0.1	0.2	0.3	0.4	0.5	0.6	0.7
Probability of continuing enrollment	98%	90%	74%	54%	34%	18%	7%

To assess for potential delayed radiation toxicities, a 6-month safety visit will be performed. Patients who stop protocol therapy before the 6 months post stereotactic radiation treatment visit will be evaluated by phone by a member of the study team. If at any point during the trial the risk of delayed radiation toxicity is deemed to be excessive, the trial will be terminated.

In addition to the safety run-in in the first 6 patients treated, a continual assessment of symptomatic necrosis at 6 months and at 1 year will be conducted, using the method of Ivanova, et al (25) that applies Pocock-style boundaries for the maximum-tolerated rates of toxicity. Specifically, rates of necrosis at 6 months that are 25% or greater or at 1 year that are 50% or greater are considered unacceptable. For each toxicity rule, the upper limit of the probability of early stopping,  $\phi$ , is set at 0.1 and the proportion with maximum-tolerated toxicity,  $\theta$ , is defined as half the unacceptable rate. The following gives the sequential stopping rules tabulated according to the number of events. For instance, if 3 events of symptomatic necrosis at 6 months are observed in the first 6 patients enrolled, or if 8 events are observed in the first 30 patients, the study would be terminated for excessive toxicity.

Boundary for necrosis at 6 months	3	4	5	6	7	8	9	10	11
Maximum number enrolled	≤6	≤10	≤14	≤19	≤25	≤30	≤36	≤41	≤47
Boundary for necrosis at 1 year	5	6	7	8	9	10	11	12	13
Maximum number enrolled	≤8	≤10	≤13	≤16	≤19	≤21	≤24	≤27	≤30
Boundary for necrosis at 1 year	14	15	16	17	18	19			
Maximum number enrolled	≤34	≤37	≤40	≤43	≤46	≤47			

The probabilities of stopping the trial early for vary true rates of each classification of toxicity are presented below:

True rate of necrosis at 6 months	Prob of stopping early, $\phi$	E[N]	True rate of necrosis at 1 year	Prob of stopping early, $\phi$	E[N]
0.125	0.0994	43.91	0.25	0.1000	43.93
0.20	0.4708	34.48	0.30	0.2529	40.06
0.30	0.9169	18.94	0.40	0.7254	27.13
0.40	0.9966	10.40	0.50	0.9692	15.43
0.50	1.0000	6.64	0.60	0.9993	9.32

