## 13. STATISTICAL CONSIDERATIONS

### 13.1 Study Design/Endpoints

This is an open-label, single arm phase II study to assess PFS in patients with TNBC and brain metastasis who will receive stereotactic radiation in combination with atezolizumab. The target enrollment is 45 participants.

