### Radiation Necrosis

Brain metastases treated with stereotactic radiation which enlarge post treatment will be evaluated for radiation necrosis by the treating radiation oncologist, via neuroradiology assessment, and/or through the use of dual-phase PET-CT studies (Horky *et al.*, 2011), as clinically indicated, according to standard of care. The cumulative incidence of necrosis will be evaluated as the time from first dose of atezolizumab (day 1 cycle 1) to detected necrosis. Patients without detected necrosis will be censored at the end of the study, whether due to death or other reason. Cumulative incidence will be analyzed using Kaplan–Meier product-limit estimates and will be plotted with two-sided 90% confidence bands using Greenwood’s formula for the variance.

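### The necrosis stopping-rule table in 13.4 assumes outcomes known at once, so at 2 patients a month its E[N] greatly understates how many are enrolled before the rule stops the trial

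*Combined protocol and SAP*

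**What the plan says.** Section 13.4 states that "a continual assessment of symptomatic necrosis at 6 months and at 1 year will be conducted", using a Pocock-style boundary for each horizon. It declares that "rates of necrosis at 6 months that are 25% or greater or at 1 year that are 50% or greater are considered unacceptable". The tolerated rate is half of each, 12.5% and 25%, and the probability of stopping at the tolerated rate is capped at 0.1.

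The rule counts events among patients in order of enrolment: "For instance, if 3 events of symptomatic necrosis at 6 months are observed in the first 6 patients enrolled, or if 8 events" in the first 30 would end the trial. The boundary rows are labelled "Maximum number enrolled" and run to 47. The lowest listed counts are 3 events at 6 months and 5 events at 1 year. The second table, introduced with "The probabilities of stopping the trial early for vary true rates of each classification of toxicity are presented below", gives a stopping probability and E[N] for five true rates per rule. E[N] is not defined.

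Elsewhere, 13.1 says "The target enrollment is 45 participants" and 13.2 says "Anticipated accrual of approximately 2 patients per month, it will require approximately 24 months of patient accession to reach 45 patients". Section 5.2.4.1.8 places the necrosis visits 5 to 8 and 11 to 14 months after radiation. On necrosis, 13.7 says "Patients without detected necrosis will be censored at the end of the study, whether due to death or other reason".

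**The concern.** The outcomes take 6 and 12 months to mature, and patients enter at about 2 a month. No accrual hold for pending necrosis outcomes is planned. By the time the deciding event is known, many more patients have been treated than the number on which the boundary was crossed. A table built as though outcomes were immediate cannot show this.

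The table is the plan's only quantified statement of how many patients are exposed before excessive late necrosis stops the trial. A safety committee or ethics board reading it would expect about 15 patients at a 50% 1-year rate. Three further gaps limit its use:

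- It has no row at 25% for 6 months, the rate 13.4 itself calls unacceptable.
- It tabulates the two rules separately although they run together.
- It does not say how patients who die, or are still in follow-up, before 6 or 12 months are counted.

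**Working it through.** **Inputs.** From 13.4, listed boundaries (events: largest n at which they stop the trial):

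- 6 months: 3:6, 4:10, 5:14, 6:19, 7:25, 8:30, 9:36, 10:41, 11:47.
- 1 year: 5:8, 6:10, 7:13, 8:16, 9:19, 10:21, 11:24, 12:27, 13:30, 14:34, 15:37, 16:40, 17:43, 18:46, 19:47.

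From 13.1 and 13.2: N = 45, 2 patients a month.

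**Step 1: reproduce the printed table.** Let b(n) be the smallest event count whose listed maximum is at least n, and S(n,k) the probability of k events after n patients without having stopped. With every outcome known before the next entry,

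S(n,k) = (1−p)·S(n−1,k) + p·S(n−1,k−1) for k < b(n),

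P(stop) = 1 − Σₖ S(N,k), and E[N] = Σ over n = 0 to N−1 of Σₖ S(n,k).

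Adding boundaries of 2 events in 2 patients (6 months) and of 3 in 3 and 4 in 5 (1 year), with N = 47, gives the third column. These extra boundaries are inferred from the fit; the plan does not state them.

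| Rule, true rate | Printed P / E[N] | N = 47 with extra boundaries | N = 47, listed only | N = 45, listed only |
|---|---|---|---|---|
| 6 mo, 12.5% | 0.0994 / 43.91 | 0.0992 / 43.91 | 0.0919 / 44.29 | 0.0888 / 42.46 |
| 6 mo, 20% | 0.4708 / 34.48 | 0.4706 / 34.46 | 0.4642 / 34.99 | 0.4417 / 33.88 |
| 6 mo, 30% | 0.9169 / 18.94 | 0.9167 / 18.92 | 0.9155 / 19.43 | 0.8985 / 19.24 |
| 1 yr, 25% | 0.1000 / 43.93 | 0.1000 / 43.94 | 0.0896 / 44.47 | 0.0880 / 42.65 |
| 1 yr, 50% | 0.9692 / 15.43 | 0.9695 / 15.41 | 0.9688 / 16.35 | 0.9639 / 16.28 |

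All ten printed rows agree with the third column within 0.0005 in P and about 0.02 in E[N]. For the listed boundaries at N = 45, the largest change in P is 0.4708 − 0.4417 = 0.029. So 47 versus 45 and the unlisted boundaries matter little by themselves. The omitted row, 25% at 6 months, gives P = 0.7204 and E[N] = 26.12 at N = 45.

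**Step 2: add the delay.** If outcomes are known only at the horizon, the number enrolled when a boundary is met on n patients is about min(45, n + 2 × D). That adds 2 × 6 = 12 patients for the 6-month rule and 2 × 12 = 24 for the 1-year rule. Even the smallest listed 1-year count could not stop the trial before about 5 + 24 = 29 are enrolled (27 with the inferred 3-in-3 boundary).

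The more favourable case counts events as they occur. This was simulated: 40,000 replicates, one entry every 0.5 month, listed boundaries, N = 45, no deaths. Crossing was taken as the earliest calendar time at which events among the first n patients reach the boundary. In each range the first figure counts events as they occur, with uniform timing over the window; the second counts them only at the visit.

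| Each rule alone | Printed E[N] | Expected enrolled | Printed P(stop) | P(stop before 45 enrolled) |
|---|---|---|---|---|
| 6 mo, 25% | none | 30.7–34.1 | none | 0.66–0.59 |
| 6 mo, 30% | 18.94 | 24.9–29.4 | 0.9169 | 0.85–0.80 |
| 6 mo, 50% | 6.64 | 13.4–19.2 | 1.0000 | close to 1 |
| 1 yr, 40% | 27.13 | 37.3–41.1 | 0.7254 | 0.52–0.41 |
| 1 yr, 50% | 15.43 | 30.6–37.4 | 0.9692 | 0.85–0.73 |

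**Step 3: both rules together.** At 50% by 1 year with uniform timing, 26.4–31.6 are enrolled and P(stop before 45) is 0.89–0.82. If every event falls after month 6, the figures are 33.5–37.4 and 0.81–0.73. At the tolerated rates (12.5% and 25%), the probability of crossing either boundary is 0.14. The plan does not state this; its cap of 0.1 applies to each rule separately.

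**Step 4: deaths.** Section 13.6.2 uses median OS of 5 months (null) and 10 months (alternative). Under exponential survival, 0.5^(12/5) = 0.19 to 0.5^(12/10) = 0.44 of patients are alive at 12 months. Assume a 50% 1-year necrosis rate on the death-censored scale of 13.7, deaths kept in n as non-events, uniform timing, events counted as they occur, and both rules in force. Then P(ever crossing) is 0.28–0.57, against 0.97 without deaths, and about 35–39 patients are enrolled.

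**The case against.** The strongest reply is that the table contains no calculation error. It reproduces, it is the standard output for this type of boundary, and E[N] may mean patients evaluated. That is fair as to the arithmetic. But E[N] is undefined, the rule and its boundary rows speak of patients enrolled, and nothing warns the reader that enrolment will run well past E[N].

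Several narrower points stand in part:

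- Setting 15.43, a single-rule figure, against 26–37 for both rules mixes two settings. The like-for-like range is 30.6–37.4, so the mixed comparison understates the gap.
- The run-in on the first 6 patients implies a short hold that the simulation omits; it is worth about one patient.
- The no-death figures are conditional. Deaths make the position worse.
- The 25% row is bracketed by 20% and 30%, so its absence is a lesser gap.
- Section 13.7 summarises any detected necrosis, while 13.4 monitors symptomatic necrosis. The two need not share a censoring rule, but 13.4 still needs one of its own.

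The probability of ever crossing changes by at most 2.9 points without deaths, and at the tolerated rates E[N] is about right. Committee review up to four times a year (12.2) and the general clause in 13.4 on excessive delayed toxicity are real safeguards, but neither has stated operating characteristics.

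**Conclusion.** The concern holds. At the elevated rates where the rule is meant to act, the printed E[N] is far below the number who would be enrolled: for the 1-year rule at 50%, 30.6–37.4 against 15.43, a factor of 30.6/15.43 = 2.0 to 37.4/15.43 = 2.4. For the 6-month rule at 30%, it is 24.9–29.4 against 18.94, a factor of 1.3 to 1.6. Part of the printed stopping probability is realised only after all 45 are enrolled.

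These figures rest on 2 entries a month, no accrual hold for necrosis outcomes, events counted in enrolment order, no deaths, and event timing that the plan does not give (hence the ranges). The delay is the material defect. The mismatch of 47 with 45 and the unlisted boundaries are minor, and the latter are inferred. The handling of deaths could matter as much as the delay, because it affects whether the rule stops the trial at all.

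**What to change.** Keep the boundaries. In 13.4:

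1. State that n means the first n patients in enrolment order and that events count as they occur.
2. State how patients who die, or are still in follow-up, before 6 or 12 months are counted, and reconcile this with the censoring in 13.7.
3. Replace the table. For N = 45 at 2 a month with both rules in force, give P(ever crossing), P(stop before full enrolment) and expected number enrolled, over a range of event timings and death rates, with a 25% row for 6 months.
4. End the boundary tables at 45 and print every boundary used.

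The cost is a statistician's recalculation, two clarifying sentences and a replaced table. The stated exposure becomes less favourable. No extra patients, visits or procedures are needed.
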